- 1) Descriptive analyses (frequency tables) will present, by month, the absolute numbers of contraceptive counseling visits, LARC consultations (with a scheduled insertion) (overall, and by LARC type [contraceptive implant, IUD]); and initiations (overall, and by LARC type [items 1-3 above]).
- 2) Descriptive analyses will present the proportion of LARC initiations out of the number of contraceptive counseling visits [item 4], contraceptive initiations for all methods [item 5], and telehealth-based LARC consultations [item 6]. A consultation is defined as a visit for which a LARC initiation was

scheduled. These analyses will be presented in frequency tables.

3) For each of the uptake outcomes listed above [items 4-7], bivariate statistical analyses will compare the outcome proportions for contraceptive implant vs. IUD, using Chi-square tests.

Aim 1.2 Bivariate analyses will assess the uptake of LARC methods (overall, and contraceptive implant vs. IUD) by patient subgroup, examining LARC initiation (in absolute numbers, and as a proportion of telehealth consultations) by patient characteristics (age, race/ethnicity, gender identity, sexual orientation, sexual activity in last 90 days, gravidity, parity).

Statistical Methods (Aim 1.2)

Bivariate Chi-square tests will compare the proportion who initiated out of those who had 1) a telehealth contraceptive counseling consultation and 2) a LARC consultation for which an insertion was scheduled across subgroups defined by age group (using age categories consistent with the CDC's Youth Behavior Risk Surveillance System, ages 13-14, 15-17, 18-19, 20 and older); race/ethnicity (Hispanic + Black, Black non-Hispanic, Hispanic of any other race, non-Hispanic race other than Black); gender identity (female, male, transmale, gender non-conforming); sexual orientation (straight/heterosexual, gay/lesbian, bisexual, asexual); sexual activity (any/no sexual activity in last 90 days); gravidity (any/no pregnancy history); parity (any/no live birth).

Aim 2: Describe the implementation of telehealth-supported long-acting reversible contraception (LARC) service provision in school-based health centers (SBHCs) using mixed methods.

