Thematic analysis will be used to describe the qualitative data generated from the interviews. Using an inductive approach, two coders will scan a random selection of transcripts to generate initial codes; working from these, we will generate a code-book that lists major themes, specifies categories

emerging from the data, and descriptions of each theme. The first 10 transcribed interviews will be jointly coded using Dedoose; then, inter-rater coding agreement will be assessed. The entire study team will: resolve discrepancies in coding, clarify theme definitions, and collapse or expand themes as needed.

Primary efficacy outcome (Aim 3): Continuation post-LARC initiation

The primary outcome for this study (3.1) will be absolute continuation rate 12 months post-initiation (dichotomous yes/no continuation), with analyses also examining continuation at 6 months (yes/no).

Aim 3.1 (Primary Efficacy Outcome): Overall 12-month continuation of LARC using telehealth-supported care compared to LARC continuation rates among adolescents age 25 and under as documented in a meta-analysis of US studies.

The primary outcome will be the proportion of patients continuing their initiated LARC method at 12 months post-initiation. Hypothesis: We hypothesize that, with the non-inferiority margin of 10 percentage point difference, in this sample of adolescents receiving telehealth-supported LARC services in a network of SBHCs, the LARC continuation rate at 12 months will be non-inferior to the reported 12-month continuation rate among adolescents and young adults age under 25 years (85.3%) in the US who initiated contraceptive implants or IUDs the absence of telehealth (Usinger, Gola, Weist & Smaldone, 2016).

Statistical Methods (Aim 3.1):

Continuation rates will be expressed as rates at both 6 months and 12 months post initiation, and time to discontinuation will be visualized using Kaplan-Meier curves.

We will test the primary null hypothesis $H_0: p \leq 0.753$ (i.e., 10 percentage points less than the reference rate of 0.853) using one-sample, one-tailed Z-test, where p is the LARC continuation rate at 12 months for participants who receive telehealth-supported LARC services in a network of SBHCs, and the reference the proportion (of 0.853) was chosen from the finding of the meta-analysis mentioned above.

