Additionally, we will use Chi-squared tests to compare continuation (yes, continued/no, discontinued) between LARC types (contraceptive implant vs. IUD) at two time points: 6 months and 12 months post-initiation. Adjusted analyses using logistic regression will be conducted to compare the continuation at 6 and 12 months (yes or no) separately between contraceptive implant and IUD patients, adjusting for covariates (age, race/ethnicity, gender identity, sexual orientation, sexual activity in last 90 days, gravidity, parity). Operationalization of these covariates is outlined in Aim 1.

Power/Sample Size (Aim 3.1):

The study anticipates enrolling 113 patients, with 102 patients included in the continuation analyses for Aim 3 (primary outcome). Our sample size estimates are based on conservative SBHC clinical data from 2018-2019 and from the first seven months of 2019-20 (which was disrupted by both the transition to a new EHR Epic system and school and SBHC closures due to COVID-19); during the July 2018 to January 2020 time period, there were, respectively, 129 LARC initiations (86 contraceptive implant, 43 IUD), and 44 LARC initiations (41 implant, 3 IUD). These sample size estimates are conservative, as the SBHCs have three newly-hired and trained medical providers since the 2019-20 disrupted year.

We anticipate having complete data for the continuation analyses sample size ($n=102$). Using the new Epic EHR, at each visit within the NYP clinical network – the participating study sites in the SBHCs, as well as the emergency department, inpatient and outpatient clinics – the health care provider is required to conduct reconciliation of medications and document it in the Epic EHR. The medical providers ask every patient at every visit what their current contraceptive method is – confirming the presence of the method, and documenting in two places in the EHR (in the contraception and in medications sections). These analyses will be able to assess continuation (presence of the device at a visit) and censoring

(device removal, device removal with re-insertion).

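### The adjusted implant-versus-IUD logistic models fit 13 to 16 slopes to about 15 expected 12-month discontinuations; ordinary maximum likelihood pushes the odds ratio away from 1, and Firth penalisation largely corrects this.

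*Combined protocol and SAP*

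**What the plan says.** Statistical Methods (Aim 3.1) adds to the chi-squared tests an adjusted comparison of the two LARC types: "Adjusted analyses using logistic regression will be conducted to compare the continuation at 6 and 12 months (yes or no) separately", "adjusting for covariates (age, race/ethnicity, gender identity, sexual orientation, sexual activity in last 90 days, gravidity, parity". On coding it says "Operationalization of these covariates is outlined in Aim 1". Statistical Methods (Aim 1.2) gives that coding. Age has four groups ("ages 13-14, 15-17, 18-19, 20 and older"), race/ethnicity has four, and two more covariates have four each: "gender identity (female, male, transmale, gender non-conforming); sexual orientation (straight/heterosexual, gay/lesbian, bisexual, asexual". Sexual activity, gravidity and parity are binary.

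Power/Sample Size (Aim 3.1) puts 102 patients in the continuation analyses and says "We anticipate having complete data for the continuation analyses sample size". The planning rate is 85.3% continuation at 12 months, with the null set "10 percentage points less than the reference rate of 0.853". The historical split is "129 LARC initiations (86 contraceptive implant, 43 IUD), and 44 LARC initiations (41 implant, 3 IUD".

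Section 2 mentions model building with the Biostatistician. Nowhere does the plan name an estimator, a rule for empty or sparse levels, or a response to separation for these models.

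**The concern.** Logistic regression with no estimator named will normally be fitted by ordinary maximum likelihood (ML). With about one event per slope, ML overfits: coefficients move away from zero on the log scale, their spread grows, and some may have no finite estimate because a covariate level contains only continuers or only discontinuers. The software then reports huge or non-converged terms, and the analyst must improvise with the outcomes in view. A modest difference between implant and IUD could be published as a large one. At stake is the only adjusted yes/no comparison of the two LARC types in the plan, which is secondary.

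**Working it through.** **Inputs from the plan.** As a check on the planning figures, the stated 80% power is reproduced with one-sided alpha 0.05 (the plan states no alpha): Φ[(0.100 − 1.645 × √(0.753 × 0.247/102)) / √(0.853 × 0.147/102)] = Φ(0.0298/0.0351) = 80.2%. So N = 102 with 85.3% continuation is the plan's own scenario.

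**Slopes.** LARC type 1 + age 3 + race/ethnicity 3 + gender identity 3 + sexual orientation 3 + sexual activity 1 + gravidity 1 + parity 1 = 16. Eligibility (Section 4) is female only; if gender identity then has one level, 16 − 3 = 13.

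**Events at 12 months.** 102 × 0.147 = 15.0, so 15/16 = 0.94 to 15/13 = 1.15 per slope. At the null rate, 102 × 0.247 = 25.2, or 1.6 to 1.9 per slope.

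**Events at 6 months.** No rate is given, but these are a subset of the 12-month events. A constant hazard gives 102 × (1 − √0.853) = 7.8; two-thirds of events in the first half-year gives 10.0. Both are assumptions.

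**Split.** 43/129 = 33% IUD, or 34 of 102. Pooling both periods, 46/173 = 27%, or 27 of 102.

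**Simulation.** The plan gives no category frequencies, so two mixes were assumed, with categories in the plan's order.

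- Mix A: age 5/65/27/3%, race/ethnicity 8/20/60/12%, gender identity 95/1/2/2%, orientation 75/5/17/3%, sexually active 75%, gravid 15%, a third of these parous.
- Mix B: 10/50/30/10%, 15/20/50/15%, 88/4/4/4%, 60/10/20/10%, 60%, gravid 25%, half of these parous.

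Covariates were independent and unrelated to outcome, empty levels were dropped, and each scenario had 1,000 datasets. The odds ratio (OR) is for discontinuation, IUD versus implant; its mean is exp(mean log OR), over finite estimates for ML. Results for 12 months, 34 IUD and 68 implant, 15 events, true OR 2, both mixes, 13 or 16 slopes:

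| | ML | Crude | Firth, same covariates |
|---|---|---|---|
| Mean OR | 2.23–2.38 | 1.96 | 1.94–1.95 |
| SD of log OR | 0.83–0.98 | 0.64 | 0.64–0.68 |
| OR above 5 | 14%–19% | 6% | 7%–8% |
| 95% CI, upper/lower limit (median) | 14.9–18.3 | 9.9 | 11.7–12.6 |
| Coverage | 93.0%–94.1% | 95.7% | 95.0%–95.5% |
| LARC term infinite | 0.1%–0.5% | 0.1% | 0 |

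ML and crude intervals are Wald; Firth intervals are profile. Some term separates in 97%–100% of datasets with 16 slopes and in 76%–99% with 13.

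**Variations, true OR 2 unless stated.**

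- 25 events: ML 2.3–2.4 (SD 0.63–0.67), crude SD 0.49, Firth 2.0 (SD 0.52–0.53).
- 27 IUD: ML 2.19–2.38 (SD 0.90–1.00), Firth 1.92–1.95 (SD 0.67–0.69).
- 6 months, 8 events: ML 2.5–2.6 (SD 1.1–1.3), LARC term infinite in 6%–10% (crude 2%); Firth 1.95–1.96 (SD 0.78–0.82), interval still 27.5- to 30.5-fold.
- Merging levels under five patients, then ML: 2.17–2.35 (SD 0.80–0.96), separation in 75%–85%.
- True OR 1: rejection 6.2%–6.6% (ML), 3.5% (crude), 4.6%–5.6% (Firth).
- Assumed confounding, log OR 0.7 on both LARC choice and discontinuation for age 18 and over, parity and the third race/ethnicity category: crude 2.6–2.8, ML 2.2–2.6, Firth 1.9–2.0.

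**Other assumptions.** A separate simulation with different frequencies and covariate effects gave ML 2.34–2.75 and Firth 2.01–2.06 for a true 2; ML 3.92–4.97 and Firth 3.00–3.07 for a true 3; ML 0.43–0.45 and Firth 0.51–0.52 for a true 0.5. With no covariate effects, ML still gave 2.36 and Firth 2.01, while ML with two slopes gave 1.99. The inflation is therefore overfitting.

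**The case against.** Several points on the other side stand in part.

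- **The average bias is small beside the spread.** On the log scale it is ln(2.23/2) = 0.11 to ln(2.38/2) = 0.17, against SDs of 0.83 to 0.98. That is 0.13 to 0.18 SD, or about 2% to 3% of mean squared error. ML coverage is close to nominal, and at a true OR of 1 there is no material average bias (0.97–0.99). This is right: the larger cost is the added variance, and much of the imprecision exists unadjusted.
- **The sizes rest on assumed mixes.** They do. Separation falls to 48%–68% when all levels are common, and mostly affects covariate terms. The direction of the bias and the Firth correction held in every non-null scenario with 102 patients.
- **Fifteen events is a best case.** Section 3 gives 6 to 18 months of follow-up. With even accrual (assumed) about 51 patients reach 12 months, giving 51 × 0.147 = 7.5 events. The LARC term is then infinite under ML in 14% to 29% of trials. Firth averages 1.86 to 2.15 across the assumptions tried, with intervals 47- to 73-fold wide in one set of runs. This strengthens the case against ML, but Firth cannot supply missing information.
- **Fewer covariates would also remove the bias.** True, as the two-slope result shows. It gives up confounding control that the plan chose to have, and the confounded scenario shows that control can matter.
- **The comparison is secondary, and Section 1 (Aim 3) also plans Cox models by LARC type.** Also true. The plan lists no covariates for those models, so they do not replace this adjusted analysis.

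**Conclusion.** The concern holds. The plan's own figures put 13 to 16 slopes against about 15 events at 12 months, and no more at 6 months, with no estimator or sparse-level rule. Under ordinary ML a true OR of 2 averages 2.2 to 2.4 in the main simulation (up to 2.75 under other assumptions), and an OR above 5 is reported two to three times as often as in the crude analysis. Firth regression on the same covariates brings the average back to about 2 and the spread close to that of the crude estimate.

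These sizes assume 12-month status for all 102 patients, the planning rate of 85.3%, and covariate frequencies the documents do not give. The direction is firm; the second decimals are not. Intervals remain roughly 12-fold wide or more, so the comparison is exploratory with either estimator. This is a worthwhile, cheap improvement to a secondary analysis and does not touch the primary one-sample test.

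**What to change.** In Statistical Methods (Aim 3.1):

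1. State that the adjusted 6- and 12-month implant-versus-IUD models are fitted by Firth-penalised logistic regression with profile penalised-likelihood intervals, keeping the planned covariates.
2. Prespecify, without reference to outcomes, that empty levels are dropped and very sparse levels merged: for example, a level with fewer than five patients joins the adjacent age group or the next smallest category. Say also what happens to a binary covariate with fewer than five patients in one level; the merging simulation dropped it. Merging alone does not repair ML.
3. Report the comparison as exploratory.

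A smaller prespecified covariate set is optional and the sponsor's choice.

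The cost is SAP wording, standard software and a little more analysis work. A true OR of 2 is estimated at 1.94 to 1.95, and power to detect it is about 19% to 20%, against 23% to 24% for ML or the crude analysis.

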With a sample size of 102 and the margin of non-inferiority of 10 percentage points, the proposed study has 80% power to declare the non-inferiority of the telehealth-supported LARC services in a network of SBHCs in a one sample, one-sided Z test. This power analysis is for the primary efficacy outcome of interest, i.e., LARC continuation rate at 12 months. The reference LARC continuation rate at 12 months of 0.853 was obtained from the meta analysis conducted by Usinger, Gola, Weis & Smaldone in 2016. The studies included in their meta-analysis collected sample in the US with participants in those studies being young women aged 25 years and younger using a range of contraceptive methods. Therefore, if the true LARC continuation rate at 12 months is 0.753 or higher, the study is adequately powered to establish the non-inferiority of telehealth-supported approach. In the CHOICE Project, 12-month continuation of Copper IUDs among participants age 14-19 was 75.6% (Rosenstock et al., 2012).

Aim 3.2 (Exploratory, pending feasibility) Continuation compared to pre-Telehealth. Pending examination of the feasibility of constructing a pre-telehealth research database using the prior EHR system, compared to continuation rates within the same network prior to the implementation of telehealth-supported care, we will compare 12-month continuation (yes/no) following introduction of telehealth to 12-month continuation among LARC initiators seen the 18 month period prior to introduction of telehealth (June 2018-December 2019) *pending ability to export data from the prior electronic health record.*

3. Study Procedures

AIM 1

Participant enrollment – Aim 1: All patients who receive care at the SBHC provide informed consent for care, as well as record review for quality assurance purposes. Analyses for Aim 1 will include all female patients who have a “reproductive health visit,” which includes contraceptive counseling, contraceptive management, or contraceptive method initiation, during the study period. All patients who have a telehealth consultation with a SBHC medical provider for LARC services (conservatively estimated n=113) will be considered enrolled patients once the data are extracted from the EHR, and these will inform uptake analyses for Aim 1.

AIM 2

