Follow-up observation (Continuation Analyses, Aim 3): Follow-up observation will continue for 6 months after the enrollment phase has completed; therefore, participants enrolled in the first month will have 18 total months observation, while those enrolled in the last month will have 6 months. In 2018-19, in the network of 6 SBHCs, 2,425 unique female patients had a total of 12,398 visits (for any purpose), representing an average of 5 SBHC visits per female patient in the academic year.² At each visit to the SBHC, regardless of visit type, all female patients have their medications, including contraceptive method, reconciled and confirmed in the medical record. With the new Epic EHR system, export of all LARC-related procedure codes (insertions, removals, removal with replacement) and device codes (e.g. Nexplanon, Liletta, Paragard) *in addition to all visits* (with corresponding data on current contraceptive method) will enable us to identify person-time events including censoring. At all New York Presbyterian (NYP) sites, the health care provider is required to conduct reconciliation of medications and document it in the EHR at every visit. The SBHC medical providers ask every SBHC patient at every visit what their current contraceptive method is – confirming the presence of the method, and documenting this in two places in the EHR (in the contraception history section, and in the medications section).

Compensation.

All Aim 2 survey and interview participants will receive compensation for their time and effort in the form of an Amazon electronic gift card, purchased through the Mailman School of Public Health. Compensation is as follows:

Quantitative survey participants will receive, as compensation for their time and effort, an Amazon gift card valued at \$10 at the conclusion of the survey. The card will be sent to participants electronically.

Qualitative interview participants will receive, as compensation for their time and effort, an Amazon gift card valued at \$25. The card will be sent to participants electronically.

4. Study Subjects

Subject Population Justification:

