Adolescents and young adult high school students are the primary study participants. This study will describe in detail the implementation of a hybrid model of telehealth-supported LARC service provision in a network of 6 SBHCs in New York City that serve students who are between the ages of 13 and 22 years. The specific age range of the students was selected because it reflects the age range of students served by the 6 SBHCs. We are limiting our enrollment to high school students because the study is based in SBHCs. We have used the enrollment and retention strategies proposed in this application in our past research.

Patient population. Based on SBHC clinical data from the full academic year (2018-19), we estimate that, over the 12 month cohort there will be 113 telehealth consultations, defined as a visit in which an appointment is scheduled to initiate a LARC methods (Aim 1), and 102 LARC insertions (Aim 2). The SBHC

² This figure represents total number of visits for all patients, including patients receiving mental health care, who have regularly scheduled repeat visits. The average number of visits per year per unique female patient among LARC users is anticipated to be lower.

patient population, as a whole, is 69% Hispanic and 26% Black (not mutually exclusive), with an average age of 16 years. The majority of patients have their visits covered by Medicaid.

Participants will be eligible to participate in the study if they are: 1) an enrolled patient at the participating SBHC; 2) age 13-22 years; 3) female; 4) had a visit at the SBHC during the study period that is coded as a “reproductive health visit” including contraceptive counseling, contraceptive management, and contraceptive method initiation.

For Aims 2 and 3, individuals will be excluded if they: 1) are younger than age 13 years; 2) are older than age 22; 3) are not an enrolled patient of the participating SBHCs; 4) did not initiate a LARC method; 5) are a person without a uterus; 6) are unable to read, speak, and understand either English or Spanish.

5. Recruitment

Aim 2.1: Adolescent Survey Participants:

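### Complete month-12 data on 102 patients is unsupported, and with no status rule for patients without a late visit the primary rate can be biased in either direction

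*Combined protocol and SAP*

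**What the plan says.** **Endpoint and test** (Section 2, Aim 3.1). "The primary outcome will be the proportion of patients continuing their initiated LARC method at 12 months post-initiation". The null value is 0.753, that is, "10 percentage points less than the reference rate of 0.853", and it is tested "using one-sample, one-tailed Z-test". No alpha is stated. Kaplan-Meier curves are planned to display time to discontinuation.

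**Sample size** (Section 2, Power/Sample Size, Aim 3.1). 80% power is claimed with 102 patients "in a one sample, one-sided Z test". On missing outcomes the section says: "We anticipate having complete data for the continuation analyses sample size". Section 4 shows that the step from 113 to 102 is consultations that become insertions, so it is not an allowance for loss.

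**Ascertainment.** The same section says: "These analyses will be able to assess continuation (presence of the device at a visit) and censoring". The parenthesis that follows lists device removal, with or without re-insertion, as censoring. The source is visits at NYP sites: the SBHCs, emergency department, inpatient and outpatient clinics. Section 3 (AIM 3, Follow-up observation) adds an export of procedure codes, device codes and all visits, which "will enable us to identify person-time events including censoring".

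**Visit frequency.** Section 3 cites 12,398 visits by 2,425 female patients, about 5 each per academic year. Footnote 2 to that figure adds: "The average number of visits per year per unique female patient among LARC users is anticipated to be lower".

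The plan gives no visit window around month 12, no scheduled month-12 contact, no rule for a patient with neither a qualifying visit nor a removal code, and no missing-data method. The Follow-Up Survey (Section 3, AIM 2) concerns the post-insertion appointment.

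**The concern.** The two outcomes do not leave equal traces. A removal inside the network is itself a visit with a code. A patient who simply keeps her device creates no record until she returns for some other reason, and the plan expects LARC users to return less often than average. The participants are high-school students, and some can be expected to graduate or transfer within a year.

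The primary result therefore depends on how patients without a late record are handled. Three conventions are open: leave them out, end their follow-up at the last visit, or count them as continuing. These move the estimate in different directions relative to a fixed bar of 0.753. A rule chosen after the data are seen could decide whether non-inferiority is declared. The problem also affects patients with a full 12 months of calendar follow-up, so it is separate from the study closing before late enrollees reach month 12.

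**Working it through.** **1. The plan's own power.** Inputs from Aim 3.1: p0 = 0.753, n = 102. Assumed because not stated: p1 = 0.853 and one-sided alpha 0.05.

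Power = Φ{[(p1 − p0) − z·√(p0(1−p0)/n)] / √(p1(1−p1)/n)}
= Φ{[0.100 − 1.645 × 0.0427] / 0.0351} = Φ(0.849) = 80.2%.

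The stated 80% reproduces, with every outcome known. At one-sided 0.025 it would be 67.9%.

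**2. Outcomes missing at random** (same formula, smaller n):

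| Missing | n | Power, 0.05 | Power, 0.025 |
|---|---|---|---|
| 0% | 102 | 80.2% | 67.9% |
| 10% | 91.8 | 75.9% | 62.5% |
| 20% | 81.6 | 70.8% | 56.5% |
| 30% | 71.4 | 64.9% | 50.0% |

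**3. Patients without a record left out.** Let v be the share of continuers confirmed and s the share of stoppers recorded (both assumed). Observed rate = p·v / [p·v + (1−p)·s].
- True 0.853, v = 0.8, s = 1: 0.682 / (0.682 + 0.147) = 0.823, n about 85, power 43%.
- True 0.853, v = s = 0.8: 0.853, no bias, power 71%.
- True 0.753, v = 1, s = 0.8: 0.753 / (0.753 + 0.198) = 0.792, false non-inferiority 21% (one-sided 0.05).

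The sign depends on whether v or s is smaller.

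**4. Follow-up ended at the last visit.** This was simulated with uniform entry, 6 to 18 months of follow-up, a constant discontinuation hazard, visits at random, removals recorded on their own date, and 15% leaving the network in year 1. For a true 85.3%, the Kaplan-Meier month-12 estimate is about 76%, 79% and 82% at 2, 3 and 5 visits per year. The removals stay in while continuers' person-time is cut short. The bias shrinks with more visits but is still present at 5.

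**5. No removal code read as continuing.** Take a true rate of 0.753 and a constant hazard, λ = −ln 0.753 = 0.284 per year. Suppose a share L leaves at a uniform time in year 1 and later stopping is unseen. The stopping hidden per leaver is (0.247/0.284) − 0.753 = 0.118, so the apparent rate is 0.753 + 0.118·L. The Z-test rejects at 84 or more of 102, or 44 or more of 51 (one-sided 0.05). Exact binomial probabilities:

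| L | Apparent rate | False non-inferiority, n=102 | n=51 |
|---|---|---|---|
| 0 | 0.753 | 5.8% | 4.3% |
| 15% | 0.771 | 12% | 8% |
| 25% | 0.782 | 19% | 11% |
| 35% | 0.794 | 28% | 15% |

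The n=51 column applies if only patients who reach month 12 before close are analysed: with uniform 12-month entry and 6 further months, 102 × 6/12 = 51.

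**The case against.** A reader might infer more than the documents support.

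- **That continuation counts only when a device is confirmed at a visit.** This is one reading of the wording. The plan does not state how a patient without a visit is classified.
- **That follow-up never asks about status, or that stopping outside the network is invisible.** SBHC providers ask the current method at every visit, and medication reconciliation covers NYP emergency, inpatient and outpatient care. A removal elsewhere is hidden only if the patient does not return to NYP, or until she does.
- **That the rate is biased in a known direction.** The mechanisms oppose each other and can cancel. Leaving out patients without a record gives no bias when continuers and stoppers are captured equally.

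The magnitudes also rest on inputs the documents do not give. Visit rates of 2 and 3 per year and exit rates of 15% to 35% are assumptions. The cited 5 per year counts SBHC visits only, while capture is wider. The Kaplan-Meier curve is a display and not the planned primary test, so item 4 shows what that reading would do, not a planned result.

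These points limit how strongly the bias can be stated. They do not supply the missing rule or support the expectation of complete data.

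**Conclusion.** The point holds in a limited form. Complete month-12 data on 102 patients is unsupported, and so is the 80% power that depends on it: about 76% with 10% missing at random and 71% with 20% (one-sided 0.05). The 12-month rate can be biased, and the plan leaves the direction open. In the illustrations, a true 85.3% reads as about 76% to 82% when follow-up ends at the last visit (2 to 5 visits per year). A true 75.3% reads as about 77% to 79% when no removal code means continuing. False non-inferiority is then about 12% to 28% at n=102, or 8% to 15% if about 51 patients reach month 12. All capture, visit and exit rates are assumptions; the documents give none for LARC users. The missing rule and the unsupported completeness follow from the text alone. It should be settled before the data are seen, because the primary conclusion depends on it.

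**What to change.** 1. **Power/Sample Size (Aim 3.1).** Replace the expectation of complete data with the expected share of patients whose month-12 status will be known. Restate power for that number, with the alpha used.
2. **Statistical Methods (Aim 3.1), Power/Sample Size and Section 3, AIM 3.** State one status rule before the data are seen:
   - A removal or changed method recorded at any NYP visit is the discontinuation event, not censoring. Say also how removal with re-insertion is classed.
   - A device confirmed at any NYP visit at or after month 12 is continuing.
   - All others are censored at data close. If the SBHC enrolment-end date can be exported, patients who have left are instead censored at the later of that date and their last NYP visit with recorded status. Patients still enrolled are not censored at their last visit.
   - The comparison with 0.753 uses the Kaplan-Meier month-12 estimate and its one-sided confidence limit, because censored patients cannot enter the binary Z-test.
3. **Sensitivity.** Report last-visit censoring as the lower result and no removal record read as continuing as the upper one. Without an exit date, the main estimate effectively coincides with the upper result, and the report should say so. State that exit censoring assumes leaving is unrelated to stopping and that stopping before exit is recorded. If 20% of stopping went unrecorded, a true 75.3% would still read as 1 − 0.247 × 0.8 = 80.2%.
4. **Month-12 question.** To detect removals elsewhere, send one status question by the existing text/email route to patients who agreed to contact.

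Cost: protocol wording, one export field if it exists, and a minor IRB amendment for the question. The effective sample becomes visibly smaller and the stated power lower.
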